5.2 EXCLUSION CRITERIA

An individual who meets any of the following criteria will be excluded from participation in this study:

An individual who meets the following criteria will be excluded from participation in this study:

1. Color blindness
2. Unable to play the video game for any reason
3. K-SADS diagnosis of clinical depression, psychosis, or Autism Spectrum Disorder
4. Has enrolled in new psychotherapy (for the treatment of a mood or anxiety disorder) or had changes to their psychotherapy in the 4-weeks prior to study enrollment
5. Endorses items #1, #2, #3, #4, #5, #6 on the C-SSRS Screener (Past-Month); i.e., has present suicidal intention/behavior.
6. Has had any changes to their medication in the 4-weeks prior to study enrollment

5.3 LIFESTYLE CONSIDERATIONS

Participants must maintain stable doses of any medication throughout participation in this study. Initiation of new medications, or substantial changes in dosage of current medications, prior to the end of the study, may be requested by the patient. In this event, the patient will be withdrawn from the study and referred to clinical care.

5.4 SCREEN FAILURES

Screen failures are defined as participants who consent to participate in this study but are not subsequently assigned to the study intervention or entered in the study. Individuals who do not meet the criteria for participation in this trial (screen failure) because of meeting one or more exclusion criteria that are likely to change over time may be rescreened. Rescreened participants will be assigned the same participant number as for the initial screening.

5.5 STRATEGIES FOR RECRUITMENT AND RETENTION

Recruitment will be mostly from participants who had already enrolled in the Parent study and who, at the time of enrollment in the parent study, had consented to be re-contacted for research purposes. All participants will be contacted via phone call or email and asked if they are interested in hearing about another research study involving a preventative intervention. If they are, we will conduct our phone screen to determine initial eligibility and whether they should be scheduled for a consent visit. After the original contact, we may also reach out to parents via text message (using a prepared and approved message template) to direct their attention to their voicemail or email, and request to schedule a phone screen. Parents of potential participants will be contacted from the sample of eligible participants of the Parent study until target enrollment of the current protocol is reached. If it is decided to recruit from outside of the Parent study, those new participants will be not be contacted via text message to complete the phone screen, as we will not have access to their contact information at that time. Only participants from the Parent study (who had consented to be re-contacted originally) will be contacted via text message).

Participants from the Parent study were initially recruited to the Parent study from outpatient psychiatry programs at the University of Michigan Health System, from multi-media advertisements (UMClinicalStudies.org, passive advertisements on social media sites and Craigslist Ann Arbor, Google Adword campaigns, print and electronic media, radio ads and flyers) and by referral from community clinicians. Participants from the Parent study can be enrolled in the current protocol if they previously endorsed elevated depressive symptoms during the Parent study and do not possess any of the exclusionary criteria. Initial screening will occur in a telephone interview. Participants can enroll in the study from anywhere in the United States, as all aspects of the study protocol will be completed remotely. Based on the demographic characteristics of the sample with elevated depressive symptoms (CDI T-scores > 50) from in the Parent study, we anticipate that the sample of the current protocol will be primarily composed of youth that identify as female (90%) and are Caucasian (75%).

If needed to reach recruitment goals, new participants may be recruited through multi-media advertisements (UMHealthResearch.org, passive advertisements on social media sites, print and electronic media, and flyers). If additional recruitment is conducted, recruitment of male youth and youth from unrepresented racial and ethnic groups will be prioritized. Additionally, recruitment outside of the Parent study will be restricted to potential participants who live in the state of Michigan, in order to ensure that an iPad can be provided to participants (via drop-off, pickup, or mail delivery) if they do not already have access to one. Interested participants (i.e., as indicated on UMHealthResearch) will fill out several pre-screen eligibility questions on UMHealthResearch. If eligible based on these pre-screening questions, participants will be contacted via phone or email to complete the phone screen.

Minimizing the potential for coercion of patients to participate: Because members of the research team are involved in clinical care and research, there is the potential that some patients of the study team may be recruited. It will be made clear to all potential subjects that participation is entirely optional and not a part of regular treatment. The bulk of the recruitment process will occur with the study coordinator, who does not treat patients in any of the clinical venues where recruitment will occur. Overall, the research team is experienced in clinical research and very mindful of the conflict between the dual roles of clinician and researcher. They firmly believe that the safety and desires of the patient take precedence over any research protocol, and work hard to assure their patients that research participation is not required for treatment. In

the case where a patient of a study team member is recruited, the consent process and signature on the informed consent document and will be obtained by the study coordinator.

Payment of participants

In the current protocol, participants will receive the following payments:

1. After completing Assessment #1 (including semi-structured interview, *Millisecond* battery, and self-report clinical measures), participants will *earn* \$50. If participants screen out during Assessment 1, participants will receive up to \$50 for their participation (according to the time spent completing the assessment; up to 2 hrs (\$25), up to 4 hours (the full \$50)).
2. After completing one half of the CCT training (2 weeks), participants will *earn* an additional \$25.
3. Once the full training has been completed (4 weeks of at least 80% compliance), participants will *earn* another \$25.
4. *After completing Assessment #2, participants will *earn* another \$25.
5. **For those who have completed Assessment #3 3-months post-intervention, participants earn an additional \$25.

Therefore, if all three assessments are completed in addition to the full EndeavorRx intervention, each participant will receive a total of \$150. All participants will have the opportunity to earn the same amount of compensation (if completed Assessment #3). Incentives are structured to promote retention of participants throughout the full intervention period, as well as for Assessment #3 (if applicable). Payment for all enrolled participants will be made in up to two payments: at payment step #4* and again at payment step #5**, if all activities completed. If participants screen out during Assessment 1, they will be provided payment after screening out. The participant will receive the incentive directly. If a participant withdraws from the study or does not complete certain parts of the study, payment will be distributed for the amount earned at the point of study discontinuation. If a participant does not complete at least 2 weeks of the CCT intervention, they will not complete the post-intervention assessments.

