1.3 SCHEDULE OF ACTIVITIES

	Pre-screening (Pre-consent)	Assessment 1 Day 1	Assessment 2 Day 60±30	Assessment 3** 150±20
Review eligibility with phone screen	X			
Informed Consent		X		
Demographics		X		
Clinical assessment				
CBCL		X		
MASC		X	X	X
CDI		X*	X	X
K-SADS (Clinical report)		X		
SCARED-P		X		X
CDSRS		X*	X	X
C-SSRS		X		
ERQ-CA		X	X	X
Behavioral assessment				
Millisecond Inquisit Web Cognitive Battery		X	X	X***
Other assessments				
ESS			X	X
Adherence Metrics from Akili			X	X
Debrief				X
Adverse Events Reporting		X	X	X

*These assessments may be administered more than once if >14 days pass before the cognitive battery and cognitive training can be administered. See Section 6.4 for additional details.

**Assessment 3 was optional to participants and then discontinued in protocol version 2.1 (02 April 2024).

***Provided iPads will be re-collected after Assessment 2. If participants do not have access to a personal tablet from which they can complete the tasks from, then they will not complete the Cognitive Battery at Assessment 3 (if applicable).

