Depressive symptoms may worsen during the course of the participation in the study, including the emergence of suicidality. During the screening period in Assessment 1, suicidal thoughts, plans, intentions and behaviors will be assessed with the Columbia-Suicide Severity Rating Scale – Screen Version (C-SSRS). If assessment uncovers suicidal plans or intentions or recent behaviors, emergency evaluation will occur, and an appropriate plan of action will be followed, e.g. safety plan will be created and referral to psychiatric emergency room. Subjects will not continue to be enrolled in the study if any items on the C-SSRS are endorsed during the screening period of Assessment 1. Therefore, any potential participant with suicidal thoughts or behaviors will be excluded from the study. Suicidal thoughts will also be assessed after the 4-week intervention and (if applicable) at a 3-month follow up through items on the CDI and CDSRS. If these items are endorsed, then evaluation will occur, followed by an appropriate plan of action (as stated above). If symptoms worsen during the course of participation, but not to the level of suicidal thoughts, plans, intentions or behaviors, the participant may be withdrawn (see 7.1 below).

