6.5.1 RESCUE THERAPY

If a participant's depression symptoms worsen over the duration of the study (as measured at Assessment #2 or spontaneously reported), the participant will be referred to receive therapy. Please refer to section 2.1.3 for additional details on the safety procedure if depressive symptoms worsen.

7 STUDY INTERVENTION/EXPERIMENTAL MANIPULATION DISCONTINUATION AND PARTICIPANT DISCONTINUATION/WITHDRAWAL

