7.1 DISCONTINUATION OF STUDY INTERVENTION/EXPERIMENTAL MANIPULATION

When a subject discontinues from CCT but not from the study, remaining study procedures will be completed as indicated by the study protocol. If a clinically significant finding is identified (including, but not limited to changes from baseline) after enrollment, the investigator or qualified designee will determine if any change in participant management is needed.

Discontinuation of study for a given participant will occur in the event of any of the following:

- Suicidal thoughts with specific plans and intentions (Endorse item 9 the CDI)
- The participant is hospitalized for any psychiatric symptoms
- A participant reports symptom worsening: > 25% increased CDI score (referenced to baseline)

Reasons for discontinuation will be documented, and all outcome assessments will proceed as scheduled, if possible.

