8.2 SAFETY ASSESSMENTS

Safety assessments include the following:

- **Columbia Suicide Severity Rating Scale** (C-SSRS), Screen Version - Recent (Posner, Oquendo et al. 2007). A clinician-rated scale assessing suicidal ideation and behavior.
- **Child Depression Inventory** (CDI). A self-report assessment to rate the severity of depression symptoms in children. Total scores on this measure range from 0 to 54. Symptom worsening: > 25% increased CDI score (referenced to baseline).

Any safety-related assessments (C-SSRS administered at Assessment #1) or primary outcome measure (CDI at Assessments #1 or #2) that are missed will be reported to the IRB as a protocol deviation. We will accept a window of \pm 1 week. However, for the other assessments, missing or late assessments will not be reported as protocol deviations unless they constitute > 50% of the total assessments. These allowances should affect neither the scientific integrity nor the safety monitoring provisions of the protocol.

All SAEs will be:

- recorded on the appropriate SAE Report Form
- followed through resolution by a study clinician
- reviewed and evaluated by a study clinician.

The study will comply with IRB reporting requirements and guidelines for SAEs.

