9.4.6 PLANNED INTERIM ANALYSES

At Time 2, after the completion of the CCT intervention, CDI scores will be evaluated across all participants. If scores are significantly worse at Time 2 than at Time 1 (a significantly higher average CDI score across participants), then the study may be halted. Similarly, if greater than one third of the participants (~7 subjects) withdraw from the study due to symptoms, then the study may be halted. If there is no change, or an improvement in CDI scores (lower CDI scores), then the study will continue as planned. This interim analysis will be conducted with the intention of maintaining safety of participants, rather than for assessing the efficacy of the intervention.

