10.1.7 CLINICAL MONITORING

No additional monitoring is required – the nature and size of this study does not require additional safety monitoring to that provided by the IRB. However, participant well-being will be monitored at both of the assessments (self-report but also clinical assessments with trained clinician). The study team will check for worsening depressive symptoms after the assessment for each participant. Video game play will also be monitored by the study team so that families can be contacted if any concern for well-being is implicated (i.e., not playing enough or playing the video game with extremely high intensity/frequency). The study team will also regularly monitor clinical self-report assessments in Qualtrics (at least 1x/week) to identify whether any safety items have been flagged in Qualtrics (Qualtrics will be set up to flag certain self-report items if endorsed).

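### Section 5.5 withholds the post-intervention assessment from anyone with under 2 weeks of training, which fits poorly with Section 7.1 and makes primary outcomes missing by adherence

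*Combined protocol and SAP*

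**What the plan says.** Section 5.5 (Payment of participants): "If a participant does not complete at least 2 weeks of the CCT intervention, they will not complete the post-intervention assessments". No exception is given.

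Section 7.1 opens by saying that a participant who stops training but stays in the study has the remaining procedures done in the way the protocol sets out. It then lists three reasons for discontinuation: endorsing CDI item 9, psychiatric hospitalisation, and a CDI rise of more than 25% from baseline. It closes: "Reasons for discontinuation will be documented, and all outcome assessments will proceed as scheduled, if possible". Neither section refers to the other.

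Section 1.3 schedules the CDI and the clinician-rated depression scale at Assessments 1, 2 and 3, and notes that Assessment 3 was dropped at version 2.1. Section 6.4 allows both scales to be repeated, but only before training begins.

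For analysis, Section 9.3 defines a complete-case population of enrolled participants with Assessment 2 data and a per-protocol set based on 80% compliance, and ranks neither. Section 9.4.1 uses listwise deletion for missing Assessment 1 or 2 data and two-sided p < 0.05. Section 9.4.2 tests CDI and the cognitive composite with paired t-tests. Section 7.2 replaces treated participants who withdraw or are discontinued from the study.

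**The concern.** Staff handling a participant who is discontinued under Section 7.1 in the first two weeks have two instructions that cannot both be followed. The Section 5.5 rule also sits in the payment text, where someone working from Sections 7 to 9 would not look for it.

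The statistical consequence goes beyond that clash. Whether a participant has a primary outcome depends, by rule, on how much they trained. If early stoppers tend to do worse, the participants left for the paired test look better than the group that started. Section 6.3 confirms there is no randomisation, so the pre-post change is itself the estimate and any selection goes straight into it. Section 9.2 says the pilot is meant to supply effect sizes for larger studies, so a distortion would carry forward. Replacement restores the number analysed but not the people lost.

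These data could often be obtained. Section 4.1 says all study activities are remote, and the bar is a rule rather than a refusal.

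**Working it through.** **Where the two rules collide.** Two of the three Section 7.1 reasons are read from the CDI. No CDI is scheduled between the start of training and Assessment 2 (Sections 1.3 and 6.4), so on schedule those two reasons arise at Assessment 2, when outcomes are already being collected. That leaves psychiatric hospitalisation, or a CDI taken off schedule, before week 2. For other early stoppers, the opening sentence of Section 7.1 refers back to the protocol and may take in the Section 5.5 bar.

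**Inputs for the size of the effect.** From the documents: a paired t-test, two-sided 5%, listwise deletion, and a target of 30 (Section 9.2). The plan gives no early-stopping rate and no SD of change, so it has no figure of its own to reproduce on this point. Assumed:
- f, the fraction of starters barred: 1/30, 0.10 or 0.20.
- δ, how much worse their change is than that of the participants assessed: 0.5 SD of change.
- True mean change over all starters: zero.

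Only loss through the bar is counted.

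**Bias.** Let m be the mean change in those assessed (positive = worse). Then (1 − f)·m + f·(m + δ) = 0, so m = −f·δ. The rejection rate comes from the noncentral t with noncentrality f·δ·√n.

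| f | bias toward benefit (SD) | in standard errors, n = 30 | rejection, n = 30 | no replacement |
|---|---|---|---|---|
| 1/30 | 0.5/30 = 0.017 | 0.09 | 5.1% | n = 29: 5.1% |
| 0.10 | 0.10 × 0.5 = 0.05 | 0.05 × √30 = 0.27 | 5.8% | n = 27: 5.7% |
| 0.20 | 0.20 × 0.5 = 0.10 | 0.10 × √30 = 0.55 | 8.3% | n = 24: 7.6% |

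With δ = 0 the bias is zero and rejection is 5.0%. With δ = −0.5 (early stoppers do better), the same 10 and 20% give 0.05 and 0.10 SD against benefit.

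If instead the barred participants are taken to worsen by 0.5 SD in absolute terms, the bias is f × 0.5/(1 − f) = 0.056 and 0.125 SD, with rejection of 6.0% and 10.2% at n = 30.

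**If only half of those barred could be reached.** The bias becomes (f/2)(1 − f)δ/(1 − f/2):
- f = 0.10: 0.05 × 0.9 × 0.5/0.95 = 0.024 SD, rejection 5.2%.
- f = 0.20: 0.10 × 0.8 × 0.5/0.90 = 0.044 SD, rejection 5.6%.

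**What an all-starter sensitivity analysis would show.** Assign worsening x to those missing Assessment 2. The estimate is −(1 − f)·f·δ + f·x.

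| f | x = 0 | x = 0.25 | x = 0.5 | zero at x = (1 − f)δ |
|---|---|---|---|---|
| 0.10 | −0.045 | −0.020 | +0.005 | 0.45 |
| 0.20 | −0.080 | −0.030 | +0.020 | 0.40 |

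Assuming no change moves 0.05 only to 0.045 SD, and 0.10 only to 0.08 SD. A range of worsening is therefore needed.

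**The case against.** A minimum-exposure rule for a post-intervention assessment is a legitimate, if debatable, choice in a non-randomised pilot. The strict contradiction affects few participants, and nothing in the documents shows that early stopping will be common or related to outcome. With one participant barred, the effect is negligible. All of this stands, and it limits the point. It does not remove it: Section 7.1 allows for assessments that prove impossible, and a planned bar is not an impossibility.

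Four stronger readings are tempting and are not supported.

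- A reader might infer that worsening in a barred participant would come to light only if volunteered, because Section 6.5.1 refers to worsening "as measured at Assessment #2 or spontaneously reported". That wording concerns referral. Section 10.1.7 has families contacted when gameplay is too low, Section 4.1 has a parent contacted after 48 hours without play, and Section 8.3.4 keeps recording adverse events after participation ends. These contacts remain, although none is a scheduled symptom measure.
- The post-intervention safety statements, "Suicidal thoughts will also be assessed after the 4-week intervention" and "The study team will check for worsening depressive symptoms after the assessment for each participant", might be read as promises to every starter. Both can be read as applying to those who reach that assessment. The same holds for the interim look: "At Time 2, after the completion of the CCT intervention, CDI scores will be evaluated across all participants".
- Section 8.2 says a "primary outcome measure (CDI at Assessments #1 or #2) that are missed will be reported to the IRB as a protocol deviation". A CDI that the protocol does not call for need not count as missed.
- A reader might infer that discontinued or replaced participants are excluded from analysis. Section 9.3 does not say so. Its complete-case population has no adherence condition, so anyone with Assessment 2 data can be included.

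It would also be too strong to say that a control arm would cure the problem, since a bar tied to training adherence need not act equally in two arms.

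**Conclusion.** The point holds in limited form. Sections 5.5 and 7.1 give opposite instructions for a small group and need reconciling, whatever the early-stopping rate turns out to be. Separately, the bar makes obtainable primary outcomes missing according to adherence, in a design where the pre-post change is the whole estimate.

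Any resulting bias is possible and modest, not demonstrated. It is 0.05 to 0.10 SD toward benefit, with 5.8 to 8.3% rejection at n = 30, if 10 to 20% are barred and are 0.5 SD worse than those assessed. With one of 30 barred it is close to nothing. It is zero if early stopping is unrelated to change, and reversed if those who feel better stop. The fraction, size and direction are all assumptions. Confidence is high for the inconsistency and the missing-by-rule mechanism, and low for any particular size of bias. It is worth correcting because the change is cheap and an Assessment 2 not collected in its window cannot be recovered later.

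**What to change.** 1. Reconcile Sections 5.5 and 7.1 so that Assessment 2 is sought, where possible, from everyone who started training, whatever amount was completed. If the sponsor keeps the bar, say so in Section 7.1 and report how many participants were barred and why.
2. Add a sensitivity analysis over all starters (at least one training session) that assigns those missing Assessment 2 no change, then a range of worsening, for example 0, 0.25 and 0.5 SD of change.
3. As clarifications only: state in Section 9.3 that the complete-case population includes discontinued and replaced participants who have data, and in Section 9.1 that compliance is reported over all starters from the automatic gameplay logs.

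Cost: wording changes and one short analysis. For an assumed 3 to 6 early stoppers (10 to 20% of 30), Assessment 2 payments are 3 × $25 = $75 to 6 × $25 = $150. At the 15 to 20 minutes per CDRS-R given in Section 8.1, clinician time is 3 × 15 = 45 to 6 × 20 = 120 minutes. Added to that are the self-reports, the cognitive battery, later return of loaned iPads and the effort of reaching disengaged families. The change estimate and the compliance rate may look less favourable.
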